7.1 NORMAL OR ADAPTIVE SYMPTOMS

Transient symptoms such as end-of-day dryness, lens awareness, itching or burning or other discomfort may occur with contact lens wear and may occasionally reduce wearing time. These are not reported as adverse events unless in the investigator's opinion they are unexpected in nature, severe or have a high rate of occurrence.

7.2 PROCEDURES FOR ADVERSE EVENTS

Treatment of an adverse event will depend on its nature and severity. Based on the clinical judgment of the investigator the participant may be referred to an ophthalmologist for treatment. The investigator will attempt to determine whether the reaction is related to the test device or a result of other factors. An adverse event form (Appendix 20 and 21) will be completed for each adverse event. If both eyes are involved, a separate adverse event form will be completed *for each eye*. Whenever possible, the adverse event will be photo-documented.

Expenses incurred for medical treatment as part of study participation will be paid by the sponsor (bills and prescription receipts kept). The participant must be followed until resolution or no further change is anticipated and/or referred for further care with the appropriate health care professional and/or recorded as being under appropriate health care as per investigator's discretion. A written report will be completed indicating the subsequent treatment and resolution of the condition.

7.3 REPORTING ADVERSE EVENTS

All potential Serious and Unanticipated Adverse Device Effects that are related or possibly related to participant's participation will be reported to the Principal Investigator and the sponsor within 24 hours of the investigator becoming aware of the event. The Investigator will report Serious Adverse

Events to the ORE within 24 hours of the investigator becoming aware of the event and as per ORE requirements (by fax, mail/delivery, phone, or email). All fatal or life threatening events will be reported immediately to the ORE.

Significant and Non-Significant Adverse Events will be reported to the sponsor as soon as possible, but no later than 5 working days after the occurrence. The Investigator will report the event to the ORE as per ORE requirements (by fax, mail/delivery, phone, or email).

Sponsor contact details are:

Contact: [name], CooperVision
Email: [contact]
[contact] / [contact]
Address: [name]

8 DISCONTINUATION FROM THE STUDY

Participants discontinued from a study will be reimbursed \$20 per hour for their active involvement in the study (including the initial screening visit). Participants will be discontinued at the discretion of the investigator, sponsor or participant. A participant's study participation may be discontinued at any time, if in the opinion of the sponsor or investigator it is in the best interest of the participant. All discontinuations will be fully documented on the appropriate study forms, including the Discontinuation Form (Appendix 18). The Discontinuation Form requires the signatures of both the participant and the investigator except where the participant is lost to follow-up in which case only the signature of the investigator is required.

The following is a list of possible reasons for discontinuation from the study:

- Screening failure: Participants will be discontinued if they do not meet the inclusion and exclusion criteria outlined in section 4.2.3.
- Unacceptable performance with products to be used in study: Participants may be discontinued if they are unable to achieve acceptable comfort and /or vision with the study products.
- Positive slit lamp finding: Participants may be permanently discontinued from the study depending on the severity of the condition and on the judgement of the investigator.

- Adverse event: If a participant experiences an adverse event during the study they may be discontinued based on the clinical judgement of the investigator.
- Symptoms: If the participant has persistent symptoms they may be discontinued based on the clinical judgement of the investigator.
- Disinterest, relocation or illness: The participant may choose to discontinue due to reasons within or beyond their control.
- Violation of protocol or non-compliance: The participant will be discontinued if they are unable or unwilling to follow the protocol specified visit schedules and/or study procedures.
- Instillation of topical ocular medication: The participant will be discontinued if they elect to use a topical ocular medication during the study unless that topical ocular medication is prescribed for a limited duration (less than two weeks) to treat a transient condition; in this case the participant may remain an active participant (at the discretion of the investigator) after stopping topical ocular medication following resolution of the ocular condition).
- Lost to follow-up: The participant will be discontinued if they cannot be contacted and do not return for a final exit visit, and if the investigator has made a reasonable effort to contact the participant for a final study visit.
- Premature termination of the study by the sponsor, the CCLR or the Office of Research Ethics at the University of Waterloo.

9 DEVICE MALFUNCTIONS

A device malfunction means the failure of the device to meet its performance specification or otherwise perform as intended. *Any defective lens that is likely to cause or contribute to a Serious Adverse Event should be reported to the Principal Investigator and sponsor **within 24 hours** of the investigator becoming aware of the malfunction. The ORE would also be notified within 24 hours of any device malfunction that may contribute to a Serious Adverse Event.*

Other defective lenses should be reported to the Sponsor as soon as possible (usually in regular study updates to the Sponsor).

This clinical study will also ascertain satisfaction and preference with subjective attributes such as comfort, dryness, vision and handling. Responses to these subjective questionnaires will not be considered as complaints or device malfunctions.

10 STUDY COMPLETION AND REMUNERATION

At the last scheduled protocol visit a study completion form (Appendix 19) will be completed, which requires the signatures of both the participant and the investigator. The participant will also be provided with a Letter of Appreciation (Appendix 17).

Once their involvement in the study is complete, participants will be informed about receiving feedback following study completion in the Letter of Appreciation.

Participant remuneration will be calculated at \$20 per hour of study visits and out-of-office tasks.

11 STATISTICAL ANALYSIS AND DATA MANAGEMENT

11.1 STATISTICAL ANALYSIS

All data will be analyzed by the CCLR at the University of Waterloo. Unmasked data analysis will be conducted using Statistica 12 and/or SPSS 24. Descriptive statistics will be provided on information regarding baseline variables (age, gender, refractive error distribution, etc.). For data completed on each eye individually (e.g. biomicroscopy), results of the right eye will be reported unless a difference between right eye and left eye is found. Table 4 lists the primary outcome variables and anticipated statistical procedures.

Table 4 : Statistical procedures

Variable	Analysis	Statistical test
Numeric rating scales Visual acuity Lens fitting Biomicroscopy (continuous variables)	Effect of lens type	Paired t-test Wilcoxon matched pairs test
Biomicroscopy (ordinal variables)	Effect of lens type	Friedman Wilcoxon matched pairs test
Subjective preference ratings Investigator refit agreement ratings	Preference of lens type	Binomial test

All data will be tested for normality of distribution using Shapiro-Wilk tests. The appropriate statistical test will be selected based on tests of normality. Statistical significance will be set at 5%, with no adjustments for multiple comparisons. In the event of missing data, individual data points will be excluded in the analysis and not extrapolated from the collected data.

A binomial test will be used to analyze the results for the count data of subjective preferences and investigator refit agreement ratings. The number of “no preference” (if featured on the scale) will be evenly distributed to the two options on the basis respondents would be equally likely to choose either.

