2 OBJECTIVES

The objective of the study is to determine if habitual or adapted contact lens wearers of Proclear 1 Day can be confidently refit into Clariti 1 Day (somofilcon A) lenses and be successful after one week of daily wear.

The primary outcome variables for this study are:

- Investigator responses to refit questions;
- Lens fit.

[REDACTED]

[REDACTED]

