3 HYPOTHESIS

The null hypothesis for this study is that there is no difference in lens fit performance between Proclear 1 Day (omafilcon A) and Clariti 1 Day (somofilcon A) lenses.

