4 MATERIALS AND METHODS

4.1 STUDY DESIGN

4.1.1 OVERALL DESIGN

This is a prospective, single-site, dispensing, bilateral wear, open label, daily wear switch study, with the test lens (Clariti 1 Day) being worn for 7 (+5) days.

Participants will attend a screening visit (Visit 1), at which consent will be obtained and eligibility to participate will be confirmed. The number of visits is dependent the participant's habitual lens type (i.e. whether it is Proclear 1 Day, or another lens type) and whether the power of the habitual lens needs to be changed. All subjects will be fit with Clariti 1 Day at the screening visit to ensure they can successfully wear the product.

Habitual wearers of Proclear 1 Day lenses will be reviewed at Visit 1 to ensure optimal visual acuity is being achieved. If the visual acuity and power of the habitual Proclear 1 Day lens is optimal, participants will be fit with Clariti 1 Day and asked to return for evaluation after 7 days of lens wear.

If an amendment of the power of the habitual Proclear 1 Day is required, participants will be dispensed with the new power of the Proclear 1 Day lenses to be worn for at least 7 days. Participants will return after wearing the Proclear 1 Day lenses to collect baseline variables. The participant will then be dispensed with Clariti 1 Day and asked to return for evaluation after 7 days of lens wear.

In the instance where the participant habitually wears lenses which are not Proclear 1 Day, the participant will be fit and dispensed Proclear 1 Day lenses to be worn for at least 7 days. After experiencing Proclear 1 Day lenses for at least 7 days, the participant will return for baseline variables to be evaluated and will be then be dispensed with Clariti 1 Day. The participant will be asked to return for evaluation after 7 days of lens wear. Participants will exit the study following the final evaluation of Clariti 1 Day.

[figure not shown]

Figure 1 Study flow chart (C1D = Clariti 1 Day; P1D = Proclear 1D). * Visit 1A applicable only if habitual Proclear 1 Day wearers require a change in lens power OR if participant is a habitual lens wearer of other types (see Section 4.4 for further details)

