4.2.3 INCLUSION AND EXCLUSION CRITERIA

A person is eligible for inclusion in the study if he/she:

1. Is at least 17 years of age and has full legal capacity to volunteer;
2. Has read and signed an information consent letter;
3. Is willing and able to follow instructions and maintain the appointment schedule;
4. Habitually wears soft spherical contact lenses with a power between +6.00 to -10.00D (inclusive) for a minimum 5 days per week, 10 hours per day **and** anticipates no difficulty wearing contact lenses for 7 days per week, 10 hours per day;
5. Habitually wears, or is able to be adequately refit into Proclear 1 Day lenses;
6. Demonstrates an acceptable fit with Proclear 1 Day and Clariti 1 Day contact lenses;
7. Is correctable to a visual acuity of 0.20 LogMAR (approximately 20/30) or better (in each eye) with the study lenses or habitual correction;
8. Manifest cylindrical spectacle refraction does not exceed -1.00DC in either eye.

A person will be excluded from the study if he/she:

1. Is participating in any concurrent clinical research study;
2. Has any known active* ocular disease and/or infection;
3. Has a systemic condition that in the opinion of the investigator may affect a study measure;
4. Is using any systemic or topical medications that in the opinion of the investigator may affect a study measure;
5. Has known sensitivity to the diagnostic pharmaceuticals to be used in the study;
6. Is pregnant, lactating or planning a pregnancy at the time of enrolment (by verbal communication);
7. Is aphakic;
8. Has undergone refractive error surgery;
9. Is an employee of the Centre for Contact Lens Research;
10. Has taken part in another clinical or (pharmaceutical) research study within the last 7 days.

* For the purposes of this study, active ocular disease is defined as infection or inflammation which requires therapeutic treatment. Mild (i.e. not considered clinically relevant) lid abnormalities (blepharitis, meibomian gland dysfunction, papillae), corneal and conjunctival staining and dry eye are not considered active ocular disease. Neovascularization and corneal scars are the result of previous hypoxia, infection or inflammation and are therefore not active.

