4.5.5.1 SPHERICAL OVER-REFRACTION WITH CONTACT LENSES

A spherical over-refraction will be conducted during the fitting of Proclear 1 Day and Clariti 1 Day for each eye to optimize the power of the lenses. Distance logMAR visual acuity will be recorded with the over-refraction. If the need to change lens power is found, a new lens with the appropriate power will be obtained. Distance logMAR visual acuity will be reassessed and a spherical over-refraction will be conducted.

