4.5.6 STUDY LENS FIT ASSESSMENT

The study lenses will be assessed for the following during the lens fit assessment at Visit 1B and Visit 3:

- Lens wettability (0-4, 0.25 steps, where 0 = excellent, 4 = very poor)
- Lens deposition (0-4, 0.5 steps, where 0 = no deposits, 4 = deposits \geq 0.5mm or film > 75% of surface)

- Decentration (optimum / decentration acceptable / decentration unacceptable)
- Corneal coverage in primary gaze (yes / no)
- Post-blink movement (0-4, 1 step, where 0 = insufficient, unacceptable movement, 2 = optimal movement, 4 = excessive, unacceptable movement)
- Tightness on push-up (0-100%, 1% steps, where 0% = falls from the cornea, 50% = optimum, 100% = no movement)
- Overall fit acceptance (0-4, 1 step, where 0 = should not be worn, 4 = perfect), providing a reason if Grade 2 or less

[Redacted]

[Redacted]

[Redacted]

[Redacted]

[Redacted]

[Redacted]

[Redacted]

[Redacted]

[REDACTED]

[REDACTED]

[REDACTED]

[REDACTED]

[REDACTED]

[REDACTED]

[REDACTED]

[REDACTED]

[REDACTED]

[REDACTED]

[REDACTED]

[REDACTED]

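### The right-eye reporting rule in Section 11.1 has an undefined exception, very probably covers the primary outcome lens fit, and by default leaves left-eye data out of the results

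*Combined protocol and SAP*

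**What the plan says.** Section 11.1 sets the rule for data completed on each eye: "results of the right eye will be reported unless a difference between right eye and left eye is found". Biomicroscopy is given as an example, not as the limit of the rule. No test, threshold, visit or lens is named for deciding that a difference exists. Nothing says whether the left eye, both eyes or a combined value is then reported. Table 4 lists comparisons by lens type and preference only, with a paired t-test or Wilcoxon test for lens fitting and no comparison between eyes. The same section says that the analysis is unmasked and uses 5% without multiplicity adjustment.

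Section 2 ("The primary outcome variables for this study are") lists investigator responses to the refit questions and lens fit. The null hypothesis in Section 3 is that "there is no difference in lens fit performance between Proclear 1 Day (omafilcon A) and Clariti 1 Day (somofilcon A) lenses".

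Wear is in both eyes. Section 4.1.1 reads: "This is a prospective, single-site, dispensing, bilateral wear, open label, daily wear switch study". Section 4.5.5.1 places an over-refraction "during the fitting of Proclear 1 Day and Clariti 1 Day for each eye to optimize the power of the lenses". The fit items in Section 4.5.6 (decentration, corneal coverage, movement, push-up tightness) each describe one lens on one cornea. Movement is scored as "Post-blink movement (0-4, 1 step, where 0 = insufficient, unacceptable movement, 2 = optimal movement, 4 = excessive, unacceptable movement", so its best value lies mid-scale; push-up tightness likewise has its optimum at 50%. Overall fit acceptance runs from 0 to 4, "providing a reason if Grade 2 or less".

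**The concern.** Naming one eye in advance is a sound way to avoid treating two eyes of one person as independent. This rule does not do that. It names the right eye subject to an exception whose trigger and consequence are both open, and those who settle them will have seen the unmasked data.

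The default also has a cost. The study asks whether wearers can be confidently refit, and a wearer needs both lenses to fit. A right-left comparison of averages can show nothing while a few individuals have a poor fit in the left eye only. Those cases would not appear in the reported fit results. The paired comparison of lenses would also rest on half of the eye data collected.

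**Working it through.** **1. Inputs.** From the documents: 67 completing participants, alpha 0.05 and power 0.80 (Sections 4.2.1 and 4.2.2), and a paired test for lens fitting (Table 4). The documents give no standard deviation, inter-eye correlation or rate of poor fit. I write ρ for the correlation between the two eyes of a participant's lens difference, and assume 0.5, 0.7 and 0.9, with equal variance and equal lens effect in both eyes.

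**2. The plan's own figure.** The 67 is for a 7-unit difference in comfort. It cannot be reproduced without a standard deviation. Solving backwards, two-sided, the SD of paired differences is 7 × √67 / (1.960 + 0.842) = 20.5 by the normal approximation, or 20.2 by the exact paired t-test. So 67 pairs detect a standardised effect of about 0.347 with 80% power. The calculation concerns comfort, so the plan claims no power for fit; 0.347 serves here only as a benchmark.

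**3. Precision.** The variance of the two-eye mean relative to one eye is (1 + ρ)/2. The information lost by using one eye is 1 − (1 + ρ)/2. The equivalent number analysed on both eyes is 67(1 + ρ)/2. The standardised effect on the mean is 0.347/√((1 + ρ)/2), with power from the noncentral t at n = 67.

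| ρ | (1 + ρ)/2 | Information lost | Equivalent n | Effect on mean | Power |
|---|---|---|---|---|---|
| 0.5 | 0.75 | 25% | 50.3 | 0.401 | 89.9% |
| 0.7 | 0.85 | 15% | 57.0 | 0.377 | 86.0% |
| 0.9 | 0.95 | 5% | 63.7 | 0.356 | 82.0% |

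**4. Type I error.** Simulation with no lens effect: 40,000 trials, n = 67, normal differences. The trigger is taken to be a 5% paired test of the right-left difference in lens effect. Simulation standard error near 5% is √(0.05 × 0.95/40,000), about 0.11 percentage points.

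| ρ | Right eye always | Left replaces right after trigger | Mean replaces right after trigger | Either eye counts after trigger | Free choice of right or left |
|---|---|---|---|---|---|
| 0.5 | 5.02% | 5.03% | 4.37% | 5.90% | 9.04% |
| 0.7 | 4.87% | 4.88% | 4.48% | 5.50% | 8.21% |
| 0.9 | 4.91% | 4.95% | 4.85% | 5.20% | 7.05% |

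The coarse 0-4 grades would change the exact percentages.

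**5. Left-only poor fits (illustration only).** With per-eye rate p and inter-eye correlation φ of poor fit, the left-only probability is q = p(1 − p)(1 − φ).

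- p = 0.01, φ = 0.7: q = 0.01 × 0.99 × 0.3 = 0.00297; 67q = 0.20; chance of at least one, 1 − (1 − q)^67, is 18%.
- p = 0.05, φ = 0.3: q = 0.05 × 0.95 × 0.7 = 0.03325; 67q = 2.23; chance of at least one is 90%.

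Both p and φ are assumed, and the range is too wide to be an estimate. It shows only that such cases, if any, would be few. The requirement of acceptable fit at entry makes the low end more plausible.

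**The case against.** The strongest reply is that a single eye is a legitimate choice and that any one-eye analysis loses this precision. That is right, and it is why the point does not call the right-eye default invalid. It does not answer the open exception, nor does it show why the cheaper use of data already collected should be declined.

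Several stronger readings are tempting, and the documents do not support them.

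- A reader might infer that left-eye data are discarded. The rule governs what is reported, its exception requires the eyes to be compared, and Section 7.2 requires an adverse event form for each affected eye. Omission is the default for results, no more.
- A reader might infer that the lens comparison is biased. The planned fit analysis is a paired comparison, and leaving out the left eye for both lenses alike does not by itself bias it.
- A reader might infer that a left-eye problem noted as a reason for a low fit grade could never reach the report. It is not known whether that reason is stored as a comment. Section 11.3 excludes comments from analysis but lets the lead investigator include relevant ones in the report. The route is discretionary, not closed.
- A reader might take it as certain that lens fit is covered. The fit form (Appendix 7) is listed without its content, so this is an inference, though a strong one. For biomicroscopy the rule applies in terms.

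Entry safeguards are real: participants must meet "Demonstrates an acceptable fit with Proclear 1 Day and Clariti 1 Day contact lenses". That criterion does not describe fit after a week of wear. The refit responses address success separately, but their content by eye is not visible.

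**Conclusion.** The concern holds. Section 11.1 leaves both the trigger and the consequence of its exception undefined, and no other section supplies them. The rule very probably reaches a primary outcome. Followed as written, it leaves collected left-eye data out of the default results.

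The size is moderate. Against the two-eye mean, one eye forgoes about 2 to 10 points of power for ρ from 0.9 down to 0.5. Type I error stays at about 5-6% if a 5% test is the trigger and is applied consistently. It reaches about 7-9% only if the choice of eye is wholly open. A reader might infer serious inflation of false positives; that would require the open choice, which the text permits but does not prescribe. All these figures rest on assumed correlations and normal differences. The number of left-only poor fits cannot be estimated from the documents. This should be corrected before analysis, but it does not undermine the design.

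**What to change.** Replace the conditional rule in Section 11.1 with one fixed in advance.

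- **Numeric per-eye variables** (wettability, deposition, monocular visual acuity, numeric biomicroscopy grades, overall fit grade): use each participant's two-eye mean per lens in the paired test of Table 4.
- **Categorical items and scales with a mid-scale optimum** (decentration, corneal coverage, post-blink movement, push-up tightness): test one eye, named unconditionally. Averaging is unsuitable here, because movement grades of 0 and 4 would average to the optimal 2.
- **Tables:** show right and left eyes separately for all fit and biomicroscopy variables, with the number of participants at Grade 2 or less for overall fit in either eye, and no extra tests.

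I would not test the worse eye or the absolute deviation from the optimum. These are trade-offs. Taking absolute deviations discards the direction, tight or loose: if one lens sits tight and the other equally loose, the two look alike and power falls to about 5%.

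The cost is a few sentences, slightly more programming and longer tables. No new data are needed if both eyes are recorded, as the rule implies. The items tested on one eye do not regain precision, but they lose the undefined trigger and their left-eye results become visible.

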4.2.2 NUMBER OF PARTICIPANTS

Participants will be recruited using CCLR records and advertising approved by the UW Office of Research Ethics (Appendices 25, 26, 27). Up to 75 participants will be dispensed with study

products, with a target of 67 completing the study. Informed consent will be obtained for all participants prior to their enrolment in the study (Appendix 1).

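### Splitting no-preference answers evenly and keeping them in n makes the preference test conservative when such answers are common, and an odd number of them has no rule

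*Combined protocol and SAP*

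**What the plan says.** Section 11.1 (Statistical analysis) states: "A binomial test will be used to analyze the results for the count data of subjective preferences and investigator refit agreement ratings". On the level it says: "Statistical significance will be set at 5%, with no adjustments for multiple comparisons". For no-preference answers, "if featured on the scale", it says the number "will be evenly distributed to the two options on the basis respondents would be equally likely to choose either". Nothing in the section removes these answers from the denominator, plans an analysis without them, or says what happens when their number is odd. The missing-data sentence in 11.1 concerns absent data points, not a recorded neutral answer. The section also says that the analysis is unmasked.

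On scope, Section 9 (Device malfunctions) says: "This clinical study will also ascertain satisfaction and preference with subjective attributes such as comfort, dryness, vision and handling". On numbers, Section 4.2.2 allows up to 75 participants to be dispensed lenses, "with a target of 67 completing the study". The questionnaires and their response options are redacted.

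**The concern.** The justification and the procedure do not match. If neutral respondents would choose at random, their choices would vary from sample to sample, and a binomial test on all n would be right. Dividing their number in half removes that variation, but the test still allows for it. The test statistic is then less variable than its reference distribution, and the more ties there are, the harder it is to declare a preference. The split share also lies closer to 50% than the share among those who choose.

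The odd-tie gap is a separate matter. One answer has to go somewhere, the lens labels are known to the analyst, and the plan leaves the choice open.

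At stake is whether real preferences on questions such as comfort, dryness, vision and handling are missed, and whether a borderline result can be reproduced from the plan alone.

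**Working it through.** **Inputs.** n = 67 (target completers) and n = 75 (maximum dispensed), from 4.2.2; level 5%, from 11.1. Null share 0.5 and a two-sided exact test are assumed, since 11.1 states neither. Tie rate t = 5–50% and preference among choosers of 2:1 or 4:1 are assumptions, because the documents give neither.

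**The plan's own figure.** Section 4.2.1 gives N = 67 for a 7-unit difference in comfort score, with no SD. It cannot be reproduced, only back-solved: SD of differences = 7 × √67 / (1.96 + 0.84) ≈ 20.5. It does not concern the preference test, for which no design figure is stated.

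**Variance.** Let A and B be the numbers preferring each lens and T the number of ties, so A + B + T = n. The split count is S = A + T/2, and S − n/2 = (A − B)/2. With no true preference, Var(A − B) = n(1 − t), so

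- true variance of S = n(1 − t)/4;
- variance used by the test = n/4.

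At n = 67 and t = 0.3 these are 67 × 0.7/4 = 11.7 and 67/4 = 16.75. The large-sample type I error is P(|Z| > 1.96/√(1 − t)): 1.9% at t = 0.3 and 0.6% at t = 0.5.

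**Exact enumeration.** All (A, B, T) outcomes were enumerated at n = 67, rejecting if p ≤ 0.05, with an odd tie going to either lens with probability 1/2.

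| Ties | Type I error, split | Type I error, dropped | Power at 2:1, split | Power at 2:1, dropped | The two odd-tie choices disagree (2:1) |
|---|---|---|---|---|---|
| 5% | 4.5% | 3.8% | 76% | 74% | 4.1% |
| 10% | 3.9% | 3.6% | 71% | 71% | 4.5% |
| 20% | 2.9% | 3.7% | 61% | 65% | 5.4% |
| 30% | 1.9% | 3.7% | 48% | 59% | 6.0% |
| 40% | 1.2% | 3.5% | 34% | 51% | 6.0% |
| 50% | 0.6% | 3.2% | 20% | 42% | 5.0% |

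- At n = 75 and 2:1, split v dropped is 72 v 76% at 10% ties, 61 v 70% at 20%, 47 v 64% at 30% and 32 v 57% at 40%.
- At 4:1 and n = 67, it is 97.7 v 99.0% at 30% ties and 78 v 94% at 50%.
- A one-sided 5% test at n = 67 shows the same pattern: type I error of 1.7–2.4% at 30% ties, depending on the odd-tie rule.
- Allocating each tie at random, which is what the stated rationale implies, would keep type I error at 4.98% at n = 67. The text, however, describes dividing the number.

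**Share.** The split share is (1 − t) × 2/3 + t/2 for a 2:1 preference. That is 65.0% at 10% ties, 61.7% at 30% and 58.3% at 50%, against 66.7% among choosers.

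**Examples, n = 67.**

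- Even number of ties: 31 v 16 with 20 ties splits to 41 v 26, p = 0.086. Dropping ties, 31 of 47 gives p = 0.040.
- Odd number of ties: 28 v 12 with 27 ties splits to 41 v 26 (p = 0.086) or 42 v 25 (p = 0.0498). Dropping ties, 28 of 40 gives p = 0.017.
- Few ties: 41 v 25 with 1 tie gives p = 0.0498 if the tie goes to the leader and 0.086 if not. Dropping it, 41 of 66 gives p = 0.064.

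If the odd tie always goes to the leading lens, type I error at n = 67 is 5.5% at 2% ties and 5.2% at 5%, slightly above nominal. The rule is therefore not conservative in every case.

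**The case against.** The strongest reply is that the rule may never be used. It applies only where a scale has the option, the scales are redacted, and Section 9 names preference topics without describing response choices. Section 2 names investigator refit responses and lens fit as the primary outcomes among its visible text, and the sample size rests on comfort scores, so no planned power for preference is lost. These points stand. They limit the importance of the concern but do not correct the rule, which the plan itself thought worth writing. No claim is made here about the refit ratings.

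It is also true that the size of the loss rests on assumed inputs. With few ties, or with a 4:1 preference and ties up to about 30%, the loss is small. A conservative test does not add false positives, and part of any exact test's shortfall is discreteness: dropping ties gives 3.2–3.8%, not 5%.

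The movement towards 50% is partly a choice of target. The split share describes all respondents, and a share among choosers can overstate how widely a lens is preferred. That is a fair reason to report the neutral proportion. It does not justify a test with the wrong variance, because both approaches address the same null of equal preference.

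Finally, the odd-tie disagreement of 4–6% is specific to 2:1. With no true preference it is 0.3–1.3% at n = 67, and at 4:1 it is 0.9% or less up to 30% ties. It also needs an odd number of ties and a borderline result. The gap nevertheless remains at any tie rate.

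**Conclusion.** The concern holds. As written, the split uses a null variance too large by a factor of 1/(1 − t), contrary to its own rationale. The error is mainly towards missing a preference. At n = 67 and a 2:1 preference the cost in power is negligible at 5–10% ties, about 4 points at 20%, 11 at 30% and 22 at 50%. At n = 75 it starts earlier, with about 4 points lost at 10% ties. The missing odd-tie rule can by itself decide a borderline result, in 4–6% of trials per question at 2:1 and n = 67.

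These sizes rest on assumed tie rates and preference strengths, a two-sided exact test against 0.5, and at least one preference scale offering the neutral option. The variance mismatch and the odd-tie gap rest on the text of 11.1 alone. This should be corrected, but it does not undermine the named primary outcomes as far as the visible text shows.

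**What to change.** Replace the splitting sentence in 11.1 along these lines: for any preference question with a no-preference option, the primary test is a two-sided exact binomial test against 0.5 among participants who state a preference; the proportions preferring Clariti 1 Day, preferring Proclear 1 Day and stating no preference are reported among all respondents with 95% confidence intervals. If the even split is kept, present it as a sensitivity analysis and state in advance where the odd answer goes.

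This costs one or two sentences and no new data. The drawback is that the test uses a smaller n and sets neutral respondents aside. Reporting their proportion makes that visible.
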